3.1.2 Intravascular Lithotripsy

Intravascular lithotripsy is a balloon-based calcium modification treatment modality that uses acoustic pressure waves to modify vessel wall calcium. Peripheral IVL is designed to improve vessel wall compliance to optimize acute gain while minimizing acute vessel injury. The safety and effectiveness of IVL has been reported in several clinical studies in moderate to severely

	No.: CP 65324	REV. D
	TITLE: Mini S Feasibility Study Protocol	
	CLASS: CLINICAL PROTOCOL	PAGE 15 OF 70

calcified PAD across multiple vessel beds [11-19], including the Disrupt PAD BTK study and the Disrupt PAD III Observational Study (OS), which evaluated peripheral IVL in BTK lesions.

The DISRUPT BTK study enrolled 20 patients with moderate to severely calcified infrapopliteal lesions with 30-day follow-up [14]. After treatment with IVL using the first generation M⁵ catheter, all patients achieved a residual stenosis <50%. There was only one type B dissection, and a total of two (2) stents were placed. These initial promising results supported the use of IVL to maximize lumen gain while minimizing dissections when treating severely calcified infrapopliteal lesions.

Introduction of the Shockwave S⁴ IVL catheter allowed for expanded treatment of BTK lesions due to a smaller crossing profile and balloon diameters relative to the M⁵ catheter. Adams et al recently analyzed a cohort of patients from the PAD III Observational Study (OS) with calcified BTK disease treated with the S⁴ IVL catheter [11]. A total of 101 patients with 114 calcified infrapopliteal arteries were enrolled at 15 sites and were followed through discharge. This study included a challenging patient and lesion cohort with 69% of patients presenting with CLI and 35% with CTO lesions. The continued safety and effectiveness of peripheral IVL was demonstrated as 99% of lesions achieved a residual stenosis < 50% with no occurrences of serious angiographic complications at the end of the procedure, regardless of BTK lesion location.

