5.2 Performance Endpoints

The performance endpoints are listed below. Device endpoints will be reported for all Mini S IVL Catheters.

- **PRIMARY: Technical Success** defined as *final* residual stenosis \leq 50% without flow-limiting dissection (\geq Grade D) of the target lesion by angiographic core lab.
- **IVL Technical Success (post-dil)** defined as *post-dilatation* residual stenosis \leq 50% without flow-limiting dissection (\geq Grade D) of the target lesion by angiographic core lab (measured immediately following mandatory post-dilatation).
- **IVL Device Success** defined as the ability to deliver, advance across the target lesion, pressurize, pulse, flush and retrieve the Mini S IVL Catheter.
- **Technical Success (final)** defined as *final* residual stenosis \leq 30% without flow-limiting dissection (\geq Grade D) of the target lesion by angiographic core lab.
- **Primary Patency** at 12 months defined as:
 - Above the knee lesions: freedom from \geq 50% restenosis as determined by Duplex Ultrasound (DUS) and freedom from Clinically-Driven Target Lesion Revascularization (CD-TLR)
 - Below the knee lesions: freedom from both total occlusion (100% diameter stenosis by DUS) in all of the target lesions in a flow pathway, as well as a CD-TLR

	No.: CP 65324	REV. D
	TITLE: Mini S Feasibility Study Protocol	
	CLASS: CLINICAL PROTOCOL	PAGE 20 OF 70

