6.5 Number of Subjects

Up to 50 subjects with a minimum of 10 BTK lesions treated with moderate to severely calcified peripheral artery disease (PAD) with a target lesion located in a native, *de novo* superficial femoral, popliteal or infrapopliteal artery will be enrolled. Up to two (2) target lesions may be treated per subject.

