7.2 Subject Selection

7.2.1 Inclusion Criteria

Subjects are required to meet all of the following inclusion criteria in order to be enrolled in the study. For lesion characteristics, each target lesion must meet eligibility. A maximum of two (2) target lesions may be treated per subject; target lesions may be in the same limb or in different limbs.

General Inclusion Criteria

1. Age of subject is \geq 18 years.
2. Subject is able and willing to comply with all assessments in the study.
3. Subject or subject's legal representative has been informed of the nature of the study, agrees to participate, and has signed the approved consent form.
4. Estimated life expectancy $>$ 1 year.
5. Rutherford Clinical Category 2, 3, 4 or 5 of the target limb(s).

Angiographic Inclusion Criteria

6. One or two target lesion(s) located in a native de novo superficial femoral, popliteal or infrapopliteal artery (above the ankle joint), in one or both limbs.

	No.: CP 65324	REV. D
	TITLE: Mini S Feasibility Study Protocol	
	CLASS: CLINICAL PROTOCOL	PAGE 22 OF 70

7. Target lesion reference vessel diameter (RVD) between 2.0 mm and 7.0 mm by investigator visual estimate.
8. Target lesion stenosis $\geq 70\%$ (for vessels below the knee, defined as P3 to the ankle joint) or $\geq 90\%$ (for vessels above the knee) by investigator visual estimate.
9. Target lesion length is ≤ 150 mm by investigator visual estimate. Target lesion can be all or part of the 150 mm treated zone.
 - Tandem lesions (lesions < 3 cm apart) are allowed if the total treated area covers the entire diseased segment. Total treated area is defined as the area treated by any device (pre-dilatation, IVL, post-dilatation, or destination therapy). Each tandem lesion/diseased segment is considered one target lesion.
 - If these segments are treated independently (i.e., no PTA treatment between two lesions) then this is considered two separate target lesions.
10. Calcification is at least moderate defined as presence of fluoroscopic evidence of calcification: 1) on parallel sides of the vessel and 2) extending $> 50\%$ the length of the lesion if lesion is ≥ 50 mm in length; or extending for minimum of 20mm if lesion is < 50 mm in length.

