9.0 DATA ANALYSIS PLAN

9.1 General Statistical Methods

Descriptive statistics will be provided in this study. Analyses will be conducted at pre-specified time points including 30 days, 6 and 12 months post procedure.

Categorical variables will be summarized by the number of observations available, frequency, and percentage. Unless otherwise noted, missing data will be excluded from the denominator. Clinical outcomes analyzed at 30 days will be evaluated as categorical (binary) data. Exact confidence intervals will be generated for estimates of proportions.

Continuous variables will be summarized by the mean, standard deviation, median, minimum and maximum. Asymptotic confidence intervals will be generated for estimates of means.

9.2 Statistical analyses will be performed using SAS System® Version 9.4 or higher. Primary Endpoints

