9.2.1 Primary Safety Endpoint

Major Adverse Events (MAE) at 30 days defined as a composite of:

- Cardiovascular death
- Clinically-driven target lesion revascularization (CD-TLR)
- Unplanned target limb major amputation (above the ankle)

SAEs will be reviewed and adjudicated by the CEC. Only those adjudicated as MAEs will comprise the composite safety endpoint.

MAEs will be assessed on a per-subject basis.

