9.2.2 Primary Performance Endpoint

Technical Success defined as final residual stenosis $\leq 50\%$ without flow-limiting dissection (\geq Grade D) of the lesion by angiographic core lab. Primary Performance will be assessed on a per-lesion basis.

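### Section 9.1 gives one exact-interval rule for all proportions, but Technical Success is counted per lesion and a subject can contribute two lesions, so that interval can be too narrow

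*Protocol*

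**What the plan says.** Section 9.1 prescribes one method for every proportion: "Exact confidence intervals will be generated for estimates of proportions". It does not distinguish the unit of analysis, and it names neither the formula nor the confidence level.

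The two primary endpoints use different units. For safety (Section 9.2.1), "MAEs will be assessed on a per-subject basis". For performance (Section 9.2.2), "Primary Performance will be assessed on a per-lesion basis". Section 6.5 adds that "Up to two (2) target lesions may be treated per subject", and Section 7.2.1 that "target lesions may be in the same limb or in different limbs". The protocol does not limit how many of the 50 subjects may have two lesions, and it does not mention dependence between lesions of one subject.

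**The concern.** An exact binomial interval is valid for independent observations. Two lesions in one subject share the patient, and usually the operator and the index procedure, so some positive correlation is plausible. The lesion count then overstates the information in the data, and the interval for Technical Success claims more precision than it has.

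Only reported precision is at stake. Even so, Section 6.2 gives the study the purpose of informing a pivotal investigation, and Section 12.9 foresees publication and regulatory submissions. An interval that is too narrow could carry into that planning. The same rule covers the secondary Technical Success endpoint with the stricter 30% threshold (Section 5.2), where success may be lower and the loss appears with fewer pairs.

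**Working it through.** The protocol states no interval width, power or success threshold, so there is no figure of its own to reproduce. The check is the true coverage of the plain interval.

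**Inputs from the protocol.** Up to 50 subjects (Section 9.3); one or two lesions each (Section 6.5); lesion as unit (Section 9.2.2). The only guide to the two-lesion share is a precedent in Section 3.1.2: "A total of 101 patients with 114 calcified infrapopliteal arteries were enrolled at 15 sites". If no patient had more than two, 114 − 101 = 13 patients had two, and 50 × 13/101 = 6.4, or about 6 of 50. This is rough: it concerns another catheter, below-the-knee disease only, and arteries instead of lesions.

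**Assumptions.** Clopper-Pearson limits; nominal 95%; number of two-lesion subjects m = 6, 10, 25 or 50; within-subject correlation ρ = 0, 0.3, 0.5 or 0.7; true success rate p in three ranges.

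**Model.** For a pair of lesions:
- P(both succeed) = p² + ρp(1 − p)
- P(neither succeeds) = (1 − p)² + ρp(1 − p)
- P(exactly one succeeds) = 2p(1 − p)(1 − ρ)

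The variance of the lesion success rate is inflated by 1 + ρ × 2m/(50 + m). At ρ = 0.5:
- m = 6: 1 + 0.5 × 12/56 = 1.11
- m = 10: 1 + 0.5 × 20/60 = 1.17
- m = 25: 1 + 0.5 × 50/75 = 1.33
- m = 50: 1 + 0.5 × 100/100 = 1.50

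**Coverage.** The exact distribution of total successes was built from 50 − m single lesions and m pairs. Its probability was summed over the totals whose interval contains p, then averaged over 101 equally spaced values of p to smooth out discreteness.

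| True success | Two-lesion subjects | ρ = 0 | 0.3 | 0.5 | 0.7 |
|---|---|---|---|---|---|
| 85-95% | 6 | 97.3% | 96.8% | 96.4% | 96.1% |
| 85-95% | 10 | 97.2% | 96.4% | 95.8% | 95.2% |
| 85-95% | 25 | 96.9% | 95.2% | 93.9% | 92.5% |
| 85-95% | 50 | 96.7% | 93.9% | 91.8% | 89.7% |
| 95-99% | 25 | 98.5% | 97.5% | 96.9% | 96.2% |
| 95-99% | 50 | 98.0% | 96.2% | 94.9% | 93.4% |
| 75-85% | 6 | 96.6% | 96.0% | 95.6% | 95.2% |
| 75-85% | 10 | 96.6% | 95.7% | 95.1% | 94.4% |
| 75-85% | 25 | 96.4% | 94.5% | 93.1% | 91.7% |

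The 75-85% range is an assumption meant only for the 30% endpoint.

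**Smallest number of two-lesion subjects at which average coverage falls below 95%:**

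| True success | ρ = 0.3 | 0.5 | 0.7 |
|---|---|---|---|
| 75-85% | 19 | 11 | 7 |
| 85-95% | 27 | 16 | 11 |
| 95-99% | never | 48 | 34 |

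**What this does to a reported interval.** Suppose 90 of 100 lesions succeed, with all 50 subjects paired. The plain interval is 82.4-95.1%. With effective n = 100/1.5 = 66.7 (ρ = 0.5) it is 80.2-96.0%, which is 1.24 times as wide. If every lesion succeeds, the lower limit is 0.025^(1/n): 96.4% for n = 100 lesions and 92.9% for n = 50 subjects.

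**The case against.** The strongest objection is that handling paired lesions is ordinary SAP detail. Section 9.1 is a general section that does not name Clopper-Pearson, and an SAP that is not shown may specify a clustered interval. That is a fair limit on what can be concluded about the final analysis. However, Section 9.1 does not defer the method. It states one rule for all proportions, and Section 9.2.2 makes one of them per lesion. As written, the rule does not fit that endpoint.

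Second, the protocol's own guides show no loss. At about 6 two-lesion subjects, average coverage stays above 96% for success rates of 85-95%. Averaging hides some low points: over success rates of 70-99%, the lowest coverage at correlation 0.5 is 94.5%, still trivial. The precedents in Section 3.1.2 report residual stenosis below 50% in all patients of one study and 99% of lesions in the other. Final success here is also judged after further IVL and destination therapy are allowed (Sections 7.7.9 and 7.7.10). Near such rates the exact interval's own conservatism largely protects it. All of this stands and keeps the point minor.

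Third, tandem lesions treated as one diseased segment count as a single target lesion (Section 7.2.1), which removes some of the pairs most likely to be correlated. This also stands, although segments treated independently still count as two.

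Fourth, an interval on an estimated effective sample size is no longer exact and adds width where little is needed. That is a real cost, quantified with the remedy.

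**Conclusion.** The concern holds in its conditional form. The plain exact interval for per-lesion Technical Success can under-cover when many subjects contribute two positively correlated lesions, and the protocol does not rule that out. At success rates of 85-95% and correlation 0.5, a loss of about one percentage point needs roughly half the subjects to have two lesions (93.9% at 25 of 50); if all do, the loss is about three points (91.8%). With few pairs, or with success near the precedent rates, there is little or no loss.

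Severity is minor. Section 9.3 confirms that there are no pre-specified hypotheses, and no success threshold uses the interval, so no decision changes. Point estimates and the per-subject interval for major adverse events are unaffected. The size rests on assumed values for the two-lesion share, correlation and success rate, and on reading the rule as a 95% Clopper-Pearson interval.

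**What to change.** Add to Section 9.1:

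> Confidence intervals for per-lesion proportions will account for clustering of lesions within subject (for example, Clopper-Pearson limits on the effective sample size, with subject as cluster). The number of subjects with two target lesions will be reported.

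If all lesions succeed, the clustered variance cannot be estimated. In that case also show the interval with the number of subjects as n, labelled as a conservative bound that assumes complete within-subject correlation.

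The method was simulated 100,000 times in each of 64 cases: success 80, 90, 95 or 98%; 6, 10, 25 or 50 pairs; correlation 0, 0.3, 0.5 or 0.7. The effective sample size was capped at the lesion count, and subjects were used as n when all lesions succeeded. Coverage was 95.1-99.5%.

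No new data are needed. The cost is width. Increase in mean width over the plain interval:

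| Success | Correlation | 6 pairs | 10 | 25 | 50 |
|---|---|---|---|---|---|
| 90% | 0 | 2% | 2% | 3% | 3% |
| 90% | 0.5 | 6% | 9% | 17% | 25% |
| 98% | 0 | 4% | 5% | 8% | 8% |
| 98% | 0.5 | 7% | 10% | 21% | 33% |

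At 98% success, coverage with the fix is near 99%, so close to the precedent rates it mostly adds conservatism.

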9.3 Sample Size Determination

Per ISO 14155:2020 (Annex I, Section 1.4), the Mini S Feasibility study is considered to be an exploratory clinical investigation that does not have pre-specified primary hypotheses. For feasibility studies, sample sizes between 12 and 50 have been recommended [21-25]. The sample size for the Mini S Feasibility study (up to n=50) is in keeping with these published recommendations.

	No.: CP 65324	REV. D
	TITLE: Mini S Feasibility Study Protocol	
	CLASS: CLINICAL PROTOCOL	PAGE 38 OF 70

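### Section 9.1 prescribes asymptotic confidence intervals for means in a study of at most 50 subjects; read in the usual way they are slightly too narrow, a minor point confined to supporting continuous summaries

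*Protocol*

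**What the plan says.** Section 9.1 of the protocol treats the two kinds of variable differently. For categorical variables: "Exact confidence intervals will be generated for estimates of proportions". For continuous variables, after listing the summary statistics: "Asymptotic confidence intervals will be generated for estimates of means". It gives no confidence level and does not say whether the multiplier comes from the normal or the t distribution.

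The sample is small. Section 6.5 has "Up to 50 subjects with a minimum of 10 BTK lesions treated" and adds "Up to two (2) target lesions may be treated per subject". Section 7.7 fixes the catheter configuration to be tried first in two consecutive blocks of 10 subjects. Under section 7.9 withdrawn subjects are not replaced, and under section 9.5 missing data are not imputed for the primary analyses.

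Both primary endpoints are yes/no outcomes. On safety, section 9.2.1 says "MAEs will be assessed on a per-subject basis"; on technical success, section 9.2.2 says "Primary Performance will be assessed on a per-lesion basis". The other endpoints listed in sections 5.1 and 5.2 are also yes/no outcomes. The study is descriptive: section 9.1 says "Descriptive statistics will be provided in this study", and section 9.3 says the investigation "does not have pre-specified primary hypotheses".

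**The concern.** An asymptotic interval for a mean ordinarily takes the normal quantile, 1.960 for two-sided 95%, and treats the estimated standard deviation as if it were known. In small samples that understates uncertainty, which is what the t quantile corrects. Section 9.1 avoids a large-sample approximation for proportions but prescribes one for means in the same small sample, and gives no reason. Because the method is stated and not left open, an analysis plan that used t intervals would depart from the protocol's wording.

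At stake is the stated precision of continuous summaries. The protocol collects such data: core-lab angiography at four timepoints for each target lesion (section 7.7.1), which yields residual stenosis, and ABI or TBI at baseline, 30 days, 6 months and 12 months (Table 1). The error always runs the same way, toward intervals that look more precise than they are.

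**Working it through.** The protocol gives no calculation for these intervals, so there is no figure of its own to reproduce. The check compares the two candidate intervals.

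**Inputs.** From the protocol: asymptotic method for means (section 9.1), at most 50 subjects, up to two target lesions each, at least 10 BTK lesions (section 6.5). Assumed: two-sided 95% level, normal quantile z = 1.960, estimated standard deviation s, independent observations. No value of s is needed, because it cancels in the comparison.

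**Formulas.**
- Normal interval: mean ± 1.960 × s/√n.
- t interval: mean ± t(0.975, n−1) × s/√n.
- Width ratio, normal to t: 1.960 / t(0.975, n−1).
- Exact coverage of the normal interval for normal data: 2 × F(1.960) − 1, with F the t distribution function on n−1 degrees of freedom.

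**Results.**

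| n | t(0.975, n−1) | Width ratio normal/t | t interval wider by | Coverage of normal interval |
|---|---|---|---|---|
| 100 | 1.984 | 0.9878 | 1.24% | 94.7% |
| 50 | 2.010 | 0.9753 | 2.53% | 94.4% |
| 40 | 2.023 | 0.9690 | 3.20% | 94.3% |
| 30 | 2.045 | 0.9583 | 4.35% | 94.0% |
| 20 | 2.093 | 0.9364 | 6.79% | 93.5% |
| 12 | 2.201 | 0.8905 | 12.30% | 92.4% |
| 10 | 2.262 | 0.8664 | 15.42% | 91.8% |

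The row n=100 is the most lesions the study could contain (50 × 2). The row n=50 is the subject cap. The row n=10 equals the minimum BTK lesion count and the size of one configuration block.

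**Check by simulation** (200,000 samples per case, nominal 95%).
- Normal data: at n=50, normal interval 94.5% and t interval 95.0%; at n=10, 91.9% and 95.1%.
- Lognormal data, sigma 0.5: at n=50, 93.5% and 94.1%; at n=10, 89.0% and 92.2%.
- Exponential data: at n=50, 93.0% and 93.6%; at n=10, 87.0% and 90.1%.

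The normal-data simulation agrees with the exact figures. With skewed data both intervals lose coverage. The t interval recovers about 0.6 points at n=50 and about 3 points at n=10, but does not return to 95%.

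**What the t interval leaves untouched.** If every subject contributed two lesions with correlation ρ, the variance of a lesion-level mean would be inflated by 1 + ρ. An interval that ignored this would use a standard error that is 1/√(1 + ρ) of the right one: 0.877 at ρ = 0.3, 0.816 at ρ = 0.5 and 0.745 at ρ = 0.8. These values of ρ are illustrative; the protocol gives none.

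**The case against.** The strongest reply is that nothing of consequence depends on a mean interval. Every listed endpoint is binary, and section 9.1 gives proportions exact intervals. Residual stenosis enters the endpoints only through the 50% and 30% cut-offs, and ABI/TBI is a visit assessment. No hypothesis, threshold or decision uses a mean interval, and the mean and standard deviation are reported anyway, so a reader can work out a t interval. This stands, and it makes the point minor.

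A second reply is that neither the normal quantile nor the 95% level appears in the text. That also stands, and both are treated here as assumptions. The normal quantile is nevertheless the ordinary reading of asymptotic, so the sentence as written points to the narrower interval.

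A reader might infer more than the protocol supports, in two ways. The first is that BTK or per-configuration means will carry intervals with only about 92% coverage. But the 10 BTK lesions are a floor and not an expected count, the blocks of 10 subjects only fix which configuration is tried first, and sections 9.1 to 9.5 specify no mean within either group. The second is that these means are what will plan the pivotal study. Section 6.2 speaks of preliminary information and of parameters for a pivotal investigation without mentioning means, and the listed endpoints that could serve as parameters are proportions.

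**Conclusion.** The sentence in section 9.1 is a poor choice for a study of this size, but the effect is small. Under the assumed normal quantile and 95% level, with normal and independent data, intervals for means are 2.5% too narrow at n=50 (coverage 94.4%) and 6.4% too narrow at n=20 (coverage 93.5%; 1 − 0.9364 = 0.064). Coverage of 91.8% is what a mean over 10 observations would give if one were reported; it describes no analysis in the protocol. Skewness would lower these figures further. The primary and listed secondary endpoints, and any conclusion drawn from them, are unaffected. This is a minor correction to supporting continuous summaries.

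**What to change.** Replace the sentence on means in section 9.1 with: *Two-sided 95% confidence intervals for means will be based on the t distribution.* This also supplies the missing confidence level for means.

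The cost is one sentence and slightly wider intervals: 2.5% at n=50, 6.8% at n=20, and 15.4% should a mean over 10 observations ever be shown. The change does not restore full coverage for skewed data, and it does not address correlation between two lesions in one subject, so a lesion-level mean with a t interval would still treat those lesions as independent.

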9.2.1 Primary Safety Endpoint

Major Adverse Events (MAE) at 30 days defined as a composite of:

- Cardiovascular death
- Clinically-driven target lesion revascularization (CD-TLR)
- Unplanned target limb major amputation (above the ankle)

SAEs will be reviewed and adjudicated by the CEC. Only those adjudicated as MAEs will comprise the composite safety endpoint.

MAEs will be assessed on a per-subject basis.

